5.1 Inclusion Criteria

Age

1. Patients must be ≥ 18 years of age at the time of signing the informed consent.

Type of Patient and Disease Characteristics

2. Patients who had a kidney transplant performed ≥ 28 days prior to enrollment.
3. BKV, based on the following criteria (both criteria a and b must be met):
 - a. Any positive whole blood or plasma BK viral load at a local laboratory obtained ≤ 90 days before the start of screening.
 - b. Confirmation of BK viremia of 350 copies/mL – 10,000,000 copies/mL as determined by the central laboratory at screening.
4. At least 1 identified, suitably matched PSL cell line for infusion is available.

Sex

5. Male and/or female

Contraceptive use by men and women should be consistent with local regulations regarding the methods of contraception for those participating in clinical studies.

- a. Male patients:

Male patients are eligible to participate if they agree to the following during the study treatment period and for at least 90 days after the last dose of study treatment:

- Refrain from donating sperm

PLUS, either:

- Be abstinent from heterosexual intercourse as their preferred and usual lifestyle (abstinent on a long term and persistent basis) and agree to remain abstinent

OR

- Must agree to use contraception /barrier as detailed below
 - Agree to use a male condom and should also be advised of the benefit for a female partner to use a highly effective method of contraception as a condom may break or leak when having sexual intercourse with a woman of childbearing potential (WOCBP) who is not currently pregnant b. Female patients:
 - A female patient is eligible to participate if she is not pregnant or breastfeeding, and 1 of the following conditions applies:

- She is a woman of non-childbearing potential (WONCBP) as defined in [Section 10.4.1](#)

OR

- She is a WOCBP and using an acceptable contraceptive method as described in [Section 10.4.2](#) during the study treatment period and for at least 90 days after the last dose of study treatment. The Investigator should evaluate the potential for contraceptive method failure (eg, noncompliance, recently initiated) in relationship to the first dose of study treatment.
- A WOCBP must have a negative highly sensitive serum pregnancy test within 21 days before the first dose of study treatment, see [Section 8.2.5](#).
- Additional requirements for pregnancy testing during and after study treatment are located in [Section 8.2.5](#).

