2.1.3 Exploratory Objectives

The exploratory objectives include comparisons of the following in recipients of PSL and in patients receiving placebo:

- To assess change in estimated glomerular filtration rate (eGFR) over 24 weeks in recipients of PSL versus placebo
- To identify changes in donor-specific anti-human leukocyte antigen (anti-HLA) antibodies in recipients of PSL versus placebo
- To determine the proportion of patients with resolution of BK viremia at 8 weeks post virus-specific T cell infusion
- To assess kidney allograft survival at 24 weeks
- To assess the incidence of recrudescent or new infections with target viruses (including cytomegalovirus [CMV]), but principally BKV
- To determine whether patients with initially low BK viral load (ie, <10,000 copies/mL) can be prevented from developing viremia \geq 10,000 copies/mL that leads to new or increased immunosuppression reduction
- To determine whether patients with initially low BK viral load (ie, <10,000 copies/mL) in the investigational arm(s) develop lower viral loads than the placebo arm

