2.3.3 Exploratory Efficacy Endpoints

The exploratory efficacy endpoints include comparison between results in patients receiving PSL versus placebo for the following:

- Change in eGFR by Modified Dose in Renal Disease (MDRD) formula.
- Changes from baseline in levels of donor-specific anti-HLA antibodies.

- Proportion of patients with resolution of BK viremia at 8 weeks post virus-specific T cell infusion.
- Proportion of patients with eGFR >20 mL/min at 24 weeks.
- Incidence of new target viral infections or recrudescent infections (i.e., BKV, CMV, EBV, AdV, JCV, and/or HHV-6) as defined by onset of viremia and/or the presence of associated symptoms relative to baseline.
- Length of BKV remission (i.e., time from clearance of BK viremia to reappearance of BK viremia (plasma viral load >156 copies/mL \times 2 measures that are at least 2 weeks apart) or end of study).
- Number of patients with screening BK viremia < 10,000 copies/mL who develop BK viremia \geq 10,000 copies/mL (sustained or non-sustained) or who experience a medically significant event that leads to changes in immunosuppression reduction.
- The absolute viral load in patients in the investigational arms versus that in patients in the placebo arm with screening BK viremia <10,000 copies/mL.

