3.4 Efficacy Analyses

This section describes the analysis to be conducted for the key secondary, other secondary and exploratory efficacy endpoint along with other endpoints. The efficacy analysis will be performed on the ITT population unless otherwise stated. Analyses using mITT may be set aside if it is determined that the ITT population and the mITT Population are identical. Unless otherwise specified, the results of efficacy analysis and all the summary tables will be presented by stratum and treatment group.

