3.4.2 Exploratory Efficacy Endpoints

Observed results, change from Baseline, and percent change from baseline for eGFR estimated by MDRD and creatinine will be summarized by visit using descriptive statistics.

Donor specific anti-HLA antibodies (DSA) (yes/no) will be summarized by visit using descriptive statistics.

Resolution of viremia will be generally defined as achieving a post-baseline viral load measure below the lower limit of quantification (<LLOQ) for that viral assay. The number of patients with resolution for each virus (BKV, CMV, EBV, AdV, JCV, and/or HHV-6) will be summarized by visit and at any visits. In addition, the proportion of patients reaching at least 1 log10 reduction or <LLOQ in BK viral load post infusion will be summarized by visit and at any visits.

LLOQ values for the viruses of interest are:

BKV Viral Load (Copy/mL): LLOQ = 156

Non-BK Target Viruses:

ADV Viral Load (Copy/mL): LLOQ = 32

CMV Viral Load (Copy/mL): LLOQ = 65.6

EBV Viral Load (Copy/mL): LLOQ = 37

HHV-6 Human Herpesvirus 6 (Copy/mL): LLOQ = 110

JCV JC Virus (IU/mL): LLOQ = 76

Time-to-event endpoints will be summarized using the Kaplan-Meier method. Number of patients with events and number of patients censored and reason of censoring will be presented along with estimate for the median time (days) and its 95% CI. Time-to-event will be presented using Kaplan-Meier plots.

Time to resolution of BK viremia will be calculated as starting at randomization for patients with detectable virus and ending at the first undetectable viral load (i.e., <LLOQ). Patients who discontinued from the study early or deceased before they are observed to have achieved resolution will be censored at the last assessment date for this endpoint.

For patients who reach the resolution of BK viremia, time to reappearance of BK viremia (duration of viral remission) will be calculated as starting at the first assessment with undetectable viral load and ending at the first detectable viral load (confirmed with 2 consecutive measures at least 8 days apart, or end of study if only one measure is available). Patients not demonstrating the reappearance of viremia would be censored on the date of the latest assessment for this endpoint. Patients who discontinued from the study early or deceased before they are observed to have will be censored at the last assessment date for this endpoint.

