Time to resolution of non-BK target viral infections (i.e., associated signs, symptoms, and presence/absence of CMV, HHV-6, EBV, JCV, and/or AdV viremia) will not be performed due to limited number of events for each virus. The time to death will not be performed but the deaths will be summarized and listed.

To evaluate the impact of missing data at some timepoints, a sensitivity analysis will also be performed on BK viremia using last observation carried forward imputation.

In addition, the number and percentage for patients will be presented for following endpoints by visit unless otherwise stated.

- Patients with eGFR >20 mL/min/1.73m² at 24 weeks
- Patients with incidence of new target viral infections or recrudescent infections (i.e., BKV, CMV, EBV, AdV, JCV, and/or HHV-6) as defined by onset of viremia.
The associated symptoms are not collected so will not be considered.
- Patients with screening BK viremia <10,000 copies/mL who develop BK viremia \geq 10,000 copies/mL (sustained or non-sustained) or who experience reduction of immunosuppression which is defined as a reduction of 50% or greater of the current dose when compared to the dose at Baseline for the following medications: tacrolimus, Prograf, Envarsus, cyclosporine, Neoral Sandimmune, everolimus, sirolimus, Rapamune, rapamycin, mycophenolate mofetil, mycophenolate sodium, mycophenolic acid, Cell Cept, Myfortic, azathioprine).
 - The following drugs would not be considered for immunosuppression reduction: Prednisone, methylprednisolone, glucocorticoids, Leflunomide, Arava, Gammagard or IVIG.

Two sets of figures will be produced for mean+/- SD for change from baseline for eGFR for (Arm 1, Arm 2 and Arm 3) and (Arm 1+2 and Arm 3).

Two sets of figures will be produced for mean+/- SD for change from baseline for Creatinine for (Arm 1, Arm 2 and Arm 3) and (Arm 1+2 and Arm 3).

Listings will be provided for viral loads, eGFR, creatinine, HLA related information and donor specific anti-HLA antibodies.

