3.4.3 Other Endpoints

Observed results, change from baseline, and percent change from baseline for eGFR (estimated by the creatinine-cystatin C method) will be summarized by visit using descriptive statistics. The number of days of hospitalizations and re-hospitalizations for any reason will be summarized.

Number and percentage for patients will be presented for following endpoints.

- Patients with biopsy-proven acute allograft rejection. The results will be provided by severity (adjudicated Banff classification)
- Patients using immunosuppressive agents, including specific immunosuppressive agents used. The doses, and any changes in dose will be listed.
- Patients with kidney injury requiring hemodialysis
- Patients with hospitalizations/re-hospitalizations for any reason

The use of antiviral therapies will be listed as concomitant medications but not summarized.

The analyses for all the efficacy endpoints are summarized in Table 1:

Table 1: Efficacy Endpoints Summary and Statistical Analysis

| Type of Endpoint | Summary Table | |
|---|------------------------|---------------------|
| | Population | Variables[*]/Method |
| Continuous | | |
| • BK viral load | Observed/Chg/Pchg | |
| • eGFR by MDRD | Observed/Chg/Pchg | |
| • eGFR by Creatinine-cystatin C | Observed/Chg/Pchg | |
| Time to event [#] | | |
| • Time to BKV resolution | Kaplan-Meier | |
| • Duration of BKV remission | Kaplan-Meier | |
| Category | | |
| • BKV resolution | Categories: Yes/No | |
| • 1 Log10 reduction of BK viral post infusion | Categories: Yes/No | |
| • Patients with screening BK viremia <10,000 copies/mL develop BK viremia ≥10,000 copies/mL | Categories: Yes/No | |
| • Donor specific anti-HLA antibodies | Categories: Yes/No | |
| • eGFR >20 mL/min/1.73m ² | Categories: Yes/No | |
| • New viral infection | Categories: Yes/No | |
| • Immunosuppression reduction | Categories: Yes/No | |
| • Immunosuppressive agents | Categories: agent type | |
| • Biopsy-proven acute allograft rejection | Categories: severity | |
| • Kidney injury requiring hemodialysis | Categories: Yes/No | |
| Category and continuous | | |
| • Hospitalizations/re-hospitalizations | Yes/No; Duration | |

N/A = Not Applicable.

[*] Chg = Change from Baseline; Pchg = Percent Change from Baseline.

[\$] Line plot will be generated.

[#] Kaplan-Meier plot will be generated for each endpoint.

[**] Ratio is defined as unique clonotype donor DNA/patient DNA*100.

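### BK recrudescence is counted over all randomised patients, so never clearing scores as a favourable No and, at similar relapse risk, the arm that clears more BK tends to look worse

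*SAP*

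**What the plan says.** The exploratory objective in SAP 2.1.3 is "To assess the incidence of recrudescent or new infections with target viruses (including cytomegalovirus [CMV]), but principally BKV". SAP 2.3.3 defines events "as defined by onset of viremia and/or the presence of associated symptoms relative to baseline". SAP 3.4.2 drops the symptom limb because symptoms are not collected, and leaves "new target viral infections or recrudescent infections (i.e., BKV, CMV, EBV, AdV, JCV, and/or HHV-6) as defined by onset of viremia". The display rule there is that "the number and percentage for patients will be presented for following endpoints by visit unless otherwise stated". Table 1 in SAP 3.4.3 lists the item as "New viral infection", with categories Yes and No.

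No denominator is written on this item. The general rule in SAP 3.4 is "The efficacy analysis will be performed on the ITT population unless otherwise stated". The next item in the same list is limited to patients with screening BK below 10,000 copies/mL; this one has no limit.

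Two other provisions matter. Protocol 5.1 requires "Confirmation of BK viremia of 350 copies/mL" or more at the central laboratory, and SAP 3.4.2 gives "BKV Viral Load (Copy/mL): LLOQ = 156". SAP 3.4.2 also plans a Kaplan-Meier analysis of time to BK reappearance among patients who reached resolution, with a confirmation rule. Table 1 lists it as duration of BKV remission.

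**The concern.** The entry floor of 350 copies/mL lies above the limit of 156, so patients start out BK viremic. An onset then needs an earlier fall below 156. The one exception is a patient whose Day 1 value has already dropped below 156 since screening.

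With ITT as the denominator, a patient who stays viremic for 24 weeks is never at risk and is counted as No, the good result. A patient who clears at Week 4 has 20 weeks in which to become a Yes. The percentage thus mixes how often patients clear with how often cleared patients relapse, and the two pull in opposite directions for an effective product. At stake is how the arms are read on an objective that the SAP says is mainly about BKV: a real reduction in relapse can be hidden, or can appear as an excess.

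**Working it through.** The documents give no clearance or relapse rate for this endpoint, so there is no planned figure to reproduce. All rates below are assumptions.

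**Identity.** Let c be the probability of clearing BK by Week 24 and r the probability of reappearance by Week 24 given clearance.

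- ITT percentage = c × r
- Percentage among patients who cleared = r
- Cleared and not recurred, out of all randomised = c − c × r
- PSL shows the higher ITT percentage when r_PSL / r_placebo > c_placebo / c_PSL

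The break-even relapse-risk ratio is 0.25/0.50 = 0.50 for 50% and 25% clearance, and 0.40/0.50 = 0.80 for 50% and 40%. At the break-even a relapse benefit is hidden; above it, the benefit is reversed.

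**Cumulative 24-week figures.** Assume exponential clearance with rate λ = −ln(1 − c)/24 and exponential relapse with weekly hazard h. Then

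c × r = 1 − (h·e^(−24λ) − λ·e^(−24h)) / (h − λ).

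For c = 0.50 and h = 0.04: λ = 0.02888, e^(−24λ) = 0.50, e^(−0.96) = 0.3829, so c × r = 1 − (0.0200 − 0.01106)/0.01112 = 0.196.

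| Clearance PSL / placebo | Hazard per week PSL / placebo | ITT % PSL / placebo | Among cleared, % | Cleared and not recurred, % of all |
|---|---|---|---|---|
| 50 / 25 | 4% / 4% | 19.6 / 9.3 | 39 / 37 | 30.4 / 15.7 |
| 50 / 40 | 4% / 4% | 19.6 / 15.3 | 39 / 38 | 30.4 / 24.7 |
| 50 / 25 | 2% / 4% | 11.4 / 9.3 | 23 / 37 | 38.6 / 15.7 |
| 50 / 40 | 2% / 4% | 11.4 / 15.3 | 23 / 38 | 38.6 / 24.7 |

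The last column is clearance minus the ITT percentage, for example 50 − 19.6 = 30.4. In the third row the relapse-risk ratio is about 0.61, above the break-even of 0.50, so PSL looks worse. In the fourth it is about 0.59, below 0.80, so PSL looks better.

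**At the planned size** (20 placebo, 40 pooled PSL). With clearance of 20% on placebo and 40% on PSL and r = 25% in both, the expected ITT counts are 20 × 0.05 = 1.0 and 40 × 0.10 = 4.0, that is 5% and 10%. From exact binomial distributions, the observed PSL percentage exceeds placebo's with probability 0.72 and ties with probability 0.11. Among cleared patients the expected figure is 25% in both arms.

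**Pooling with other viruses.** Add an independent incidence q of other-virus infection, equal in both arms, to that case. The composite is 1 − (1 − q)(1 − c × r). For q = 10% it is 14.5% on placebo and 19.0% on PSL; for q = 30%, 33.5% and 37.0%. The difference shrinks from 5.0 to 4.5 and 3.5 points but remains.

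**The case against.** The strongest reply is that the conditional analysis is already planned. The Kaplan-Meier remission analysis in SAP 3.4.2 takes only patients who resolved and reports events, censoring and reasons. Resolution is also counted by visit and at any visit. A careful reader could largely assemble the three BK states from these outputs, and non-clearance is plain in the viral load, AUC and resolution summaries. This stands in part: BK durability will not rest on the criticised item alone. But the Kaplan-Meier set is defined by a post-randomisation outcome, so it is not a comparison of the arms as randomised, and it does not correct the other display.

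Four further points stand as limits.

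- The ITT denominator comes from the general rule; it is not written on the item. Table 1 is a short list and does not fix the final layout.
- The SAP presents the item by visit. The percentages in the table above are cumulative, so they illustrate the mechanism and do not predict a planned cell.
- If onset relative to baseline (SAP 2.3.3) excludes patients viremic at baseline, almost no BK event would count and the inflation would largely vanish. The item would then fail to measure its mainly-BKV objective, so a definition is needed either way.
- The endpoint is exploratory and descriptive, and Protocol 9.1 plans no formal hypothesis testing.

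A reader might infer that an effective PSL must show more recrudescence, or about twice as much. The documents do not support that. The direction depends on the break-even ratio, the doubling comes from assuming 2:1 clearance, and with 20 and 40 patients the observed order can differ by chance. A reader might also infer a bias between arms from patients already viremic with a non-BK virus at baseline. Randomisation balances that in expectation; it lowers the level of the percentage without favouring an arm.

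**Conclusion.** The point holds in conditional form. Under the ITT default, the stated rule scores failure to clear BK as the favourable result. At similar relapse risk, the arm that clears more tends to show more recrudescence, and a true reduction in relapse is hidden or reversed unless the relapse-risk ratio is below c_placebo/c_PSL. Over the assumed scenarios with equal hazards, the ITT percentage in PSL is about 1.3 times placebo (19.6/15.3) to 2.1 times (19.6/9.3), while relapse among cleared patients is nearly equal. The result rests on three things: the ITT reading of the denominator, the reading of BK onset as a return after on-study clearance, and rates that the documents do not supply. The effect is on interpretation of an exploratory summary, not on error rates or on the primary and key secondary endpoints.

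**What to change.** In SAP 3.4.2 and Table 1:

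1. Report BKV separately from new non-BK infections.
2. Define BK recrudescence as a confirmed return to at or above LLOQ after a value below LLOQ, using the confirmation rule already in SAP 3.4.2. That rule asks for measures at least 8 days apart, whereas SAP 2.3.3 asks for at least 2 weeks; state that the former applies, or align the two.
3. Tabulate all ITT patients by arm, through Week 24, as never cleared, cleared and recurred, or cleared and not recurred. State how patients who clear and then leave early are classed, and how a Day 1 value already below 156 is handled.
4. Base the between-arm description on cleared and not recurred out of all randomised patients, beside the existing Kaplan-Meier analysis.
5. As a minor point, for each non-BK virus use patients below LLOQ at baseline as the denominator for new infection. Day 1 loads are already scheduled for all five.

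No new data are needed. The cost is SAP wording and a few more table rows.

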After the first 3 doses, patients who have undetectable BK plasma viral load at 2 or more consecutive assessments at least 2 weeks apart will discontinue PSL infusions. If a patient's viral load becomes undetectable, such a patient may be followed every 14 days for study evaluations as per the Schedule of Activities. Patients will not be permitted to receive a subsequent infusion of PSL if they develop new onset graft vs host disease (GVHD) \geq Stage 1 or cytokine release syndrome (CRS) > Grade 2 at the proposed time for infusion of any subsequent dose.

A summary of study design is shown in [Figure 1](#).

2.2.2 *Study Drug*

PSL is a third-party, donor-derived, "off-the-shelf," virus-specific T cell product with specificity for BKV, AdV, CMV, EBV, and HHV-6 (with additional cross-reactive specificity for JCV) that is cryopreserved and ready for immediate use. Cryopreservation media (without cells) will serve as the placebo and will be identical in volume and appearance when administered.

2.2.3 *Sample Size Determination*

No formal sample size determination was made for this study, whose primary endpoint is safety and tolerability. Approximately 60 patients will be randomized at approximately 38 clinical sites. Patients (n=20 in each arm) will be randomized to receive PSL (administered at a dose interval of every 14 or 28 days after 3 initial weekly doses) or placebo.

Patients will be stratified [REDACTED]

[REDACTED] A minimum of 6 patients must be enrolled in each stratum, but the remaining patients can be enrolled in either stratum.

Figure 1. Study Flow Chart

b Administrative interim analysis #1 will be performed by the Sponsor when 12 patients in Stratum 1 have completed 8 weeks in the study. Administrative interim analysis #2 will be performed when 30 patients have completed 8 weeks in the study. Interim analyses may be omitted or added at the discretion of the Sponsor to allow for long term planning, and to assess ending the study or either arm early.

Abbreviations: BKV=BK virus; Q=every; S/P=status post

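### In patients with low screening BK viral load, no planned summary counts the event in the objective: viremia of 10,000 copies/mL or more that leads to immunosuppression reduction

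*SAP*

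**What the plan says.** The objective, worded alike in protocol Section 3 and SAP 2.1.3, asks whether patients who start below 10,000 copies/mL can be kept from viremia of at least 10,000 "copies/mL that leads to new or increased immunosuppression reduction".

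The endpoint in protocol Section 3 and SAP 2.3.3 counts patients who reach 10,000, sustained or not, "or who experience a medically significant event that leads to changes in immunosuppression reduction".

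The analysis text in SAP 3.4.2 keeps the or but restates the second limb: "sustained or non-sustained) or who experience reduction of immunosuppression which is defined as a reduction of 50% or greater" of the current dose against the Baseline dose, for a named list of drugs. It requires neither a medically significant event nor a viral trigger. The endpoints in that list are presented by visit unless otherwise stated.

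SAP 3.4.3 introduces the summary table with "The analyses for all the efficacy endpoints are summarized in Table 1". One row reads "Patients with screening BK viremia <10,000 copies/mL develop BK viremia ≥10,000 copies/mL". A separate row reads "Immunosuppression reduction | Categories: Yes/No" and carries no viral load restriction. There is no row for the either/or composite and none for the two events together.

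**The concern.** The objective describes a linked event: the load rises, and immunosuppression is reduced because of it. The planned count is looser. A patient who reaches 10,000 with no drug change is an event in SAP 3.4.2 and in the Table 1 viral row, but not under the objective. A patient whose drug dose is halved for an unrelated reason, with no rise in load, is an event in the composite but not under the objective. By-visit counts of either limb cannot show whether one followed the other in the same patient.

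At stake is whether the trial can answer its own exploratory question from its planned tables, and whether a reader could mistake the composite rate for the rate of the objective's event.

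**Working it through.** **Step 1. The definitions side by side (patients with screening load below 10,000 copies/mL)**

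| Place | Event | Viremia without reduction | Reduction without viremia |
|---|---|---|---|
| Objective (protocol Section 3, SAP 2.1.3) | Viremia leading to reduction | Not an event | Not an event |
| Endpoint (protocol Section 3, SAP 2.3.3) | Viremia, or a medically significant event leading to a change | Event | Event only if such an event led to it |
| Analysis (SAP 3.4.2) | Viremia, or any reduction of 50% or more in a listed drug | Event | Event |
| SAP Table 1, viral row | Viremia | Event | Not an event |

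The Table 1 reduction row is not limited to this subset. SAP 3.4.2 is wider than SAP 2.3.3 as to cause, although it adds a size threshold and a drug list. No row or text gives the joint event.

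**Step 2. Inputs**

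The documents give no rate, subset size or power for this endpoint, so there is no figure to reproduce. Arm size is 20 ("Patients (n=20 in each arm) will be randomized to receive PSL"), and SAP 2.2.3 also says "No formal sample size determination was made for this study, whose primary endpoint is safety and tolerability". The following rates are assumptions for illustration:
- v, the proportion reaching 10,000: 0.30 placebo, 0.10 PSL.
- r, the proportion with a reduction among those who do not reach it: 0.10 to 0.30, the same in both arms.
- q, the proportion with a reduction among those who do reach it: 0.50 to 0.70, the same in both arms.

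**Step 3. Formulas and results**

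- Viral limb = v: 30% vs 10%. Ratio 0.10/0.30 = 0.33; difference 20 points.
- Either = v + (1 − v)r.
  - r = 0.10: placebo 0.30 + 0.70 × 0.10 = 37%; PSL 0.10 + 0.90 × 0.10 = 19%. Ratio 0.51; difference 18 points.
  - r = 0.30: placebo 0.30 + 0.70 × 0.30 = 51%; PSL 0.10 + 0.90 × 0.30 = 37%. Ratio 0.73; difference 14 points.
- Both = v × q.
  - q = 0.50: 15% vs 5%. Ratio 0.33; difference 10 points.
  - q = 0.70: 21% vs 7%. Ratio 0.33; difference 14 points.

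On the same placebo patients, the composite rate is 0.37/0.21 = 1.8 to 0.51/0.15 = 3.4 times the joint rate. The ratio of 0.33 for the joint event is built in by using one q for both arms.

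**Step 4. A second scenario**

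Let 30% of all patients in each arm have a reduction, and let half of the viral events lead to one. Both: 15% vs 5%. Either: placebo 0.30 + 0.30 − 0.15 = 45%; PSL 0.10 + 0.30 − 0.05 = 35%. The ratio moves to 0.35/0.45 = 0.78. The difference is 10 points under both counts.

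**Step 5. Expected counts**

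If all 20 patients per arm were in the subset, 15% vs 5% would be 20 × 0.15 = 3 vs 20 × 0.05 = 1 patients. The subset will be smaller, so the joint count will be lower still.

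**The case against.** Several points on the other side are sound. The objective is prose, and its causal phrase may only explain why 10,000 copies/mL matters. The flow chart in protocol Appendix 7 that would show the intended link is not visible. The endpoint keeps its or in protocol Section 3, SAP 2.3.3 and SAP 3.4.2. Viral loads and dose changes are both listed by patient, so joint cases could be found by hand. The endpoint is exploratory and descriptive (protocol 9.4.4), and no formal hypothesis testing is planned (protocol 9.1).

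Three stronger readings are tempting, and the documents do not support them:
- A reader might infer that the trial will report three competing rates for one question. It will not. At most two are planned, the SAP 3.4.2 composite and the Table 1 viral row; the joint event is not tabulated at all.
- A reader might infer that Table 1 contradicts SAP 3.4.2 or drops its second limb. Other Table 1 labels are shortened too: the new infection row omits recrudescence, and the 1 log10 row omits the alternative of falling below the LLOQ. The unrestricted reduction row also has its own purpose, because immunosuppression use is a separate all-patient endpoint (protocol 9.4.6, SAP 2.3.4) and SAP 3.3.6 defines a reduction for everyone.
- A reader might infer that the composite hides a PSL effect. That unrelated reductions occur equally in both arms is an assumption; protocol 4.1 and 6.8 expect that PSL may lower the number meeting criteria for reduction. No relative effect is planned, only counts and percentages. On the absolute scale the composite separates the arms at least as well as the joint event in both scenarios, though less well than the viral limb alone.

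What remains is that no planned table counts the objective's event, and that the second limb differs between SAP 2.3.3 and 3.4.2. Reading the Table 1 row as shorthand would settle neither.

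**Conclusion.** The mismatch is real and rests on the text alone. For the low viral load subset, the objective's event is never summarised, and the SAP 3.4.2 composite admits reductions that have nothing to do with viremia. The size of the effect rests wholly on assumed rates. Under the first set, the risk ratio moves from 0.33 to between 0.51 and 0.73, while the absolute difference is 14 to 18 points for the composite against 10 to 14 for the joint event. This is therefore a problem of interpretation, not a demonstrated loss of ability to separate the arms. It is worth correcting because the correction is nearly free. No alpha, power or sample size is involved, and no primary or key secondary conclusion depends on it.

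**What to change.** In SAP 3.4.2 and Table 1, for patients with screening BK viral load below 10,000 copies/mL, report per arm, at patient level over the whole study:

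- (a) viremia of 10,000 copies/mL or more;
- (b) immunosuppression reduction of 50% or more;
- (c) either, labelled as the SAP 3.4.2 composite;
- (d) viremia of 10,000 copies/mL or more followed by a reduction, labelled as the temporal proxy for the objective, since order in time does not prove cause.

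Keep the existing all-patient immunosuppression reduction row. Reconcile the second limb between SAP 2.3.3 (a medically significant event leading to a change) and SAP 3.4.2 (any reduction of 50% or more).

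The cost is SAP wording and a few table rows. The viral loads are already scheduled, and medication doses and dates are already captured (protocol 6.8). The downside is that row (d) will hold a handful of patients at most, with a wide interval, and should be read as description only.
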